### **Hypotheses**

3.1. (a) Lower testing during treatment will lead to steeper positive slopes during treatment than higher testing. The exact pattern of the treatment conditions is not predicted (e.g., low and mid better than high versus low better than mid and high versus low better than mid better than high) (b) Higher testing during treatment will lead to smaller negative slopes (i.e., less forgetting) post-treatment than lower testing. The exact pattern of the treatment conditions is not predicted (e.g., high and mid better than low versus high better than mid and low versus high better than mid better than low). 3.2. (a) Higher language (specifically vocabulary and narrative skills), working memory, and/or episodic learning scores will be associated with steeper positive slopes during treatment. (b) Better treatment learning and/or decay scores will be associated with smaller negative slopes post-treatment, indicating less forgetting. 3.3. (a) Accuracy in predicting learning outcomes will increase at each treatment point, and there will be a point during treatment when outcomes can be accurately predicted. The specific earliest point in treatment (reading 1, 2, 3, 4, or 5) when accurate predictions can be made is unknown without any specific hypothesis. (b) Accuracy in predicting retention outcomes will increase at each post-treatment point, and there will be a point during post-treatment when outcomes can be accurately predicted. The specific earliest point in post-treatment (immediate, 4-week, 8-week) when accurate predictions can be made is unknown without any specific hypothesis.

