3.1. Power Analysis for Research Question 3.1. Monte Carlo studies were conducted using Mplus to determine power to detect treatment differences in slope across 7 (treatment) or 5 (retention) data points. Slope reliabilities of .6 and .8 were considered in the specification of the population parameters. Both linear growth models and latent basis models with nonlinear growth were examined given that the expected shape of the trajectories is uncertain. Intraclass Correlation Coefficients (ICCs) from our prior studies indicated that between 10% and 30% of the variance in word learning was between persons. Thus, ICCs of both .10 and .30 were used in the power analysis. We will have .80 power or greater to detect moderate slope differences ( $d = .5$ ) between two groups of 20 individuals in the treatment phase with 7 data points. In the post-treatment phase, with 5 data points, we will have .80 power to detect slightly larger slope differences ( $d = .6$ ). Attrition has been minimal (1.9%). Thus, we will recruit additional children, as needed, to replace any children who do not complete the study. We will check the assumptions used in our power analysis yearly and update target sample size to maintain power. 3.2. Power Analysis for Research Question 3.2. Additional Monte Carlo studies were conducted using the same software, intraclass correlation coefficients, and slope reliabilities as for RQ3.1. Prior research by the team has indicated that correlations between predictors and learning are in the range of .4 and .5. Power to detect the relationship between level two predictors of this magnitude and slopes added to the treatment model will range from .70 to .85. Power to detect the main effect of each covariate at the last treatment point will similarly range from .73 to .87. Although power appears sufficient with a sample size of 60, an alternative approach if power is insufficient is to loosen our criteria for statistical significance and search for “promising” key moderators. Promising key moderators would need further testing as the

development of this treatment moves forward but would inform our understanding of which children with DLD may benefit from the treatment, addressing the research question. 3.3 There is no specific power analysis for research question 3.3.

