## Analysis Plan

### Statistical models

Research Question 3.1: We will use a multi-level modeling approach for (a) learning during treatment (7 observations: pre-treatment, repeated readings 1-6); (b) post-treatment forgetting (5 observations: reading 6, immediate, 4-week, 8-week, 12-week post). We will examine definition and naming data separately, yielding four models: treatment definition, treatment naming, post-treatment definition, post-treatment naming. For each model, observations at each test (level 1) are available for each participant (level 2). The expected shape of the trajectories is not known so the analytic approach will use either linear growth modeling or latent basis modeling, depending on which is most appropriate. Participants are randomly assigned to treatment (low, mid, high testing), and treatment will be included in the model as a fixed factor at level 2. The dependent variable is number of words correct. This count variable will likely not fit a normal distribution, and thus, an appropriate link function, such as a Poisson distribution, will be used. The research aim is to detect

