differences between treatment conditions, therefore all possible pairwise comparisons will be conducted rather than an omnibus test. The slope by treatment condition interaction will be the effect of interest in determining whether there is differential learning or forgetting across low, mid, high testing. While the focus of our analyses is on treated words, a similar modeling approach will be used to model any learning of control words during treatment. We expect relatively flat trajectories for control words in all three treatment conditions and this will allow for inferences to be made about the effect of treatment rather than development or maturation Research Question 3.2: We will add pre-treatment measures as covariates to the models used in RQ3.1 to examine the relationship between these covariates and (a) learning slopes during treatment and (b) forgetting slopes post-treatment. Recall that there are several skills relevant for learning (language, attention, working memory, episodic learning) and forgetting (treatment learning, decay) and that we have multiple measures to tap different aspects of each skill (see measured variables table). Likewise, we also will examine biological and environmental variables as predictors. Previous research has indicated that the test measures are moderately correlated at around  $r = .50$ . Since these measures are theoretically and mathematically distinct (which we will confirm via correlations), we will examine the effect of each of these predictors individually. We hypothesize that higher language, attention, working memory, and/or episodic learning scores will be associated with steeper slopes during treatment. Similarly, we hypothesize that better treatment learning and decay scores will be associated with smaller slopes, indicating less decline post-treatment. These hypotheses are consistent with theories of learning and forgetting. However, it is likely that not all of these covariates will be significantly related to performance. Research Question 3.3: We will classify responses at the end of treatment (learner vs. non-learner) and post-treatment (rememberer vs. forgetter). Then, earlier performance will be analyzed to determine when treatment and post-treatment outcomes can be predicted. This yields empirically based benchmarks for progress and an understanding of the stability of learning and forgetting over time. As with RQ 3.1 and 3.2, we will separate treatment and post-treatment data as well as definition and naming data. Within each dataset, we will classify each child as having a negative or positive outcome based on performance at the last point in the series (i.e., reading 6 for treatment, 12-month post for post-treatment). We will use the accuracy range for the untreated control words to determine the cut-offs for this classification. Then, we will select an appropriate cut-off score at each earlier point during treatment or post-treatment. Because we have decided that the cost of false positives is greater than that of false negatives (see progress report), we will select cutoffs that minimize false positives. At each test point, measures of sensitivity, specificity, and positive/negative likelihood ratios and predictive values will be calculated. We will then determine the earliest point when we can accurately predict treatment and post-treatment outcomes

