#### Follow-up analyses

The analysis plan for RQ 3.1 describes the pair-wise contrasts that will be used to follow-up on significant interactions. The analysis plan for 3.3 describes the subgroup analyses we will conduct for learners vs non-learners and forgetters vs. rememberers.

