#### Inference criteria

Likelihood ratio tests will be used to compare nested models and determine what random and fixed effects are needed for the growth models as well as the significance of the treatment effects.

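### RQ 3.1 has two incompatible rules for testing the three slope pairs and no stated alpha: about 12% v 5% false-positive risk per model at an assumed two-sided .05

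*Combined protocol and SAP*

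**What the plan says.** Children are randomised to three conditions, 20 in each. RQ 3.1 is analysed separately by phase and outcome, "yielding four models: treatment definition, treatment naming, post-treatment definition, post-treatment naming".

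Three sections bear on how a treatment difference is declared within a model:

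- **Statistical models** says that "all possible pairwise comparisons will be conducted rather than an omnibus test". The next sentence says: "The slope by treatment condition interaction will be the effect of interest".
- **Follow-up analyses** says that the RQ 3.1 plan describes the "pair-wise contrasts that will be used to follow-up on significant interactions".
- **Inference criteria** uses likelihood ratio tests to "determine what random and fixed effects are needed for the growth models as well as the significance of the treatment effects", without saying whether the treatment test is joint or pairwise.

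None of these gives alpha, sidedness or a multiplicity adjustment, and neither does any other section. The Sample size rationale mentions relaxing the significance criterion for RQ 3.2 but never states that criterion. The Analysis Plan refers to no attachment for its inference rules.

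For power, the Sample size rationale says: "We will have .80 power or greater to detect moderate slope differences". That claim is made for d = .5, comparing 20 children with 20 over the seven treatment-phase observations. The section does not give the alpha or the testing rule assumed. Under Hypotheses, for both learning and forgetting: "The exact pattern of the treatment conditions is not predicted".

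**The concern.** The first section has no gate. The second, with three conditions, is most naturally read as a joint 2-df test that must be significant before any pair is examined. The third does not settle which applies. The two rules disagree on a result that can easily occur, namely one significant pair with a non-significant interaction, and an analyst could choose between them after seeing the data.

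This matters more because the pattern across arms is left open, so any one significant pair in the predicted direction could be read as support. RQ 3.1 is the randomised comparison, and the Exploratory analysis section makes the broader vocabulary comparisons conditional on evidence from it, so the ambiguity carries forward.

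**Working it through.** **Inputs from the plan.** Three conditions, 20 children each, four RQ 3.1 models, three pairs per model.

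**Assumptions not in the plan.** Two-sided .05 per pair, no adjustment, three independent arm slope estimates with equal standard error, normal approximation.

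**The plan's own figure.** The stated power (.80 or more at d = .5, 20 v 20) cannot be reproduced from what is given. A plain two-mean formula, Φ(d√(n/2) − 1.96), gives Φ(1.58 − 1.96) = .35; one-sided .05 gives .47. Dividing d by √(1 − reliability) for the stated reliabilities of .6 and .8 gives .71 and .94. The alpha and the scale of d are not stated, so this does not show the figure to be wrong. The error rates below do not depend on it.

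**Error without a gate, all three slopes equal.** At least one pair is significant when the range of the three standardised estimates exceeds 1.96 × √2 = 2.77. The studentized range for three groups gives .122 (.121 on 57 df). Treating the pairs as independent would give 1 − .95³ = .143, which is too high because the pairs share arms. At alpha .01 the figure is .027; at .10 it is .227.

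**Error with the gate.** The 2-df test is significant when the sum of squared deviations exceeds 5.99. The range is then at least √(1.5 × 5.99) = 3.00, above the 2.77 that a pair needs. A significant gate therefore always yields at least one significant pair, and the error equals the gate's alpha, .050.

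**All rules, all slopes equal (4,000,000 simulated trials):**

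| Rule | Any false difference | Predicted direction only |
|---|---|---|
| All pairs, no gate | .122 | .066 |
| 2-df gate, then pairs | .050 | .029 |
| Holm across pairs | .044 | .024 |
| Low v high first, then the others | .050 | .025 |

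**Exactly two slopes equal.** Only one true null remains, so the error cannot exceed .050. With the third arm 1, 3 or 8 pair standard errors away: no gate .050 throughout; gate .034, .050, .050; Holm .020, .034, .050. Low v high first gives .016, .036, .050 if low is the arm that differs, and .050 throughout if mid is.

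**Power for low v high, by unadjusted power (.80 corresponds to a noncentrality of 2.80):**

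| Rule | True pattern | .80 | .85 | .90 |
|---|---|---|---|---|
| Gate | one outer arm differs | .76 | .82 | .88 |
| Gate | evenly spaced | .70 | .76 | .83 |
| Holm | one outer arm differs | .69 | .76 | .83 |
| Holm | evenly spaced | .67 | .73 | .81 |
| Low v high first | either | .80 | .85 | .90 |

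With low v high first, low v mid falls from .80 to .69 if only low differs and to .03 if only mid differs. The gate gives .76 in both cases.

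**Across the four models, all slopes equal.** With the gate at .05 in each: 1 − .95⁴ = .185 if independent, and .158 or .096 if slope estimates correlate .5 or .9 across models (assumed values). Without the gate: .407, .344, .216.

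**The case against.** The best defence is that Follow-up analyses is a loose cross-reference. It only reports what the RQ 3.1 plan says, and that plan expressly declines an omnibus test. A pairwise slope difference is itself an interaction contrast, so the plural in that section can be squared with ungated testing. That reading is possible. It still leaves three unadjusted tests per model with no stated alpha, so the higher error rate would simply be the plan's rule.

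A second objection is that the hypotheses are directional, so .066 v .029 fits the harm better than .122 v .050. That is fair for support of the hypothesis. A significant pair in the wrong direction is still a false difference, and sidedness is not stated, so both sets are given.

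A third is that .050 is too exact for a maximum-likelihood ratio test with 60 children. This stands. In a normal-slope approximation, with the statistic 60·ln(1 + 2F/57) referred to chi-square on 2 df, the gated error is about .058. Ungated z tests then run at about .131, so the contrast and the ranking of rules are unchanged. The Poisson-type and latent basis models that the plan allows were not simulated.

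Finally, a gate reverses a deliberate choice and costs power, and no within-model rule deals with the four models. Both are true. Two of the remedies below keep the ungated wording, and the four-model limit should be stated openly.

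**Conclusion.** The concern holds. The sections give different rules for declaring a pair different, and the significance level is missing altogether. If amount of testing has no effect, the chance of at least one false difference per model is about 12% under one section and 5% under the other. This assumes two-sided .05, unadjusted pairs and a normal approximation. There is no inflation above the per-pair alpha when exactly two slopes are equal. The plan should be corrected before analysis; the design itself is not in question.

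**What to change.** State alpha and sidedness, and make Statistical models, Follow-up analyses and Inference criteria give one rule within each model.

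The simplest edit is to delete the clause declining an omnibus test and write: *In each model the 2-df likelihood ratio test of slope by condition is done first at the stated alpha; only if it is significant are the three pairwise slope contrasts tested, each at that alpha.* With three arms this needs no further correction.

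Two alternatives keep the current Statistical models wording, with Follow-up analyses amended to match:

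- Holm across the three pairs.
- Low v high first at the stated alpha, and the other two pairs, each at that alpha, only if it is significant. This fits the Hypotheses section, where every example pattern has low and high differing, but it would rarely detect a difference confined to mid.

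Say that the rule controls error within each model and not across the four. In the Sample size rationale, state the alpha and rule assumed and restate power under the chosen rule.

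The cost is wording plus that restatement; added enrolment is not a necessary part of it. If unadjusted power is exactly .80, low v high loses about 4 to 10 points with the gate, 11 to 13 with Holm and none with low v high first, although low v mid then loses about 11 if only low differs. At .90 the low v high losses are 2 to 7 with the gate and 7 to 9 with Holm.

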### **Sampling Plan**

#### **Existing Data**

Registration prior to creation of data

Explanation of existing data

N/A -- Not using existing data

Data collection procedures

See attached file for details.

- [Data collection procedures.pdf](#)

Sample size

Sixty kindergarten children with DLD will participate. Children will be randomized to one of the 3 treatment manipulations (see manipulated variables) yielding 20 children per treatment condition. For each child definition and naming data will be collected for 30 treated words and 30 control words: 1 time pre-treatment, 6 times during treatment (repeated book readings 1-6), and 4 times post-treatment (immediate, 4-weeks, 8-weeks, and 12-weeks post-treatment).

Sample size rationale

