### Study design

The study is a three-group randomized design, with each participant being randomly assigned to one of three conditions. The design is mixed as there are both between participant (treatment condition) and within participant (word list) factors of interest. The factors will be counterbalanced to ensure that both word lists are represented in each treatment condition. Additional notes on blinding of research personnel who interact directly with subjects: The research assistant who administers the treatment cannot be blind to the treatment condition. They must know the treatment condition to correctly deliver it. This same research assistant collects during treatment because it would be cost prohibitive to send a second research assistant to every treatment to collect these data. Blinding of research personnel occurs in the following ways: (1) The research assistant (RA) administering pre- and post-treatment testing is blind to condition assignment to reduce bias. (2) All tests are scored by RAs who are blind to the treatment condition to reduce bias.

*No files selected*

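### Treated-word growth is attributed to treatment because control words are expected to look flat, with no treated-versus-control slope contrast planned

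*Combined protocol and SAP*

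**What the plan says.** The combined protocol and SAP, under Sample size, states: "For each child definition and naming data will be collected for 30 treated words and 30 control words". Testing takes place once before treatment, six times during it and four times after it, so both word types are observed on 1 + 6 + 4 = 11 occasions.

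Statistical models, Research Question 3.1, separates the data by phase and outcome, "yielding four models: treatment definition, treatment naming, post-treatment definition, post-treatment naming". Testing condition enters as follows: "treatment will be included in the model as a fixed factor at level 2". The target is given as "The slope by treatment condition interaction will be the effect of interest". The section says that its focus is on treated words.

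For control words it adds that "a similar modeling approach will be used to model any learning of control words during treatment". It continues: "We expect relatively flat trajectories for control words in all three treatment conditions", and says that this will allow "inferences to be made about the effect of treatment rather than development or maturation".

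Study design describes "within participant (word list) factors of interest", and Randomization assigns each child to one of two treated word lists. Statistical models, Follow-up analyses and Inference criteria contain no treated/control term, no comparison of treated with control slopes, and no definition of flat. The only other stated use of control words is in Research Question 3.3, where their accuracy range sets the classification cut-offs for both phases.

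**The concern.** The plan states a causal inference, treatment rather than maturation, and collects within-child data suited to testing it. The described analysis then stops at looking at the control line. Failure to detect a control slope does not show that the slope is zero. A clear slope for one word type beside an unclear one for the other is not a test of the difference between them. That difference is the quantity the inference needs.

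Two things are at stake. One is the supporting claim that treated words grew because of treatment. The other is how far a difference between testing conditions reflects learning of the treated words, as opposed to a general effect of more testing, such as readier responding, that would raise both word types. After treatment, general vocabulary growth could partly hide forgetting of treated words, and a model of treated words alone would not show it.

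**Working it through.** **The plan's own figure.** None is given for a treated-versus-control contrast. The nearest is power of .80 or more for a between-condition slope difference of d = .5 with two groups of 20. A plain two-sample normal formula at two-sided 0.05 gives 0.35. The plan's figure came from Mplus simulations whose alpha and standardiser for d are not reported, so this is a failure to reproduce, not proof of error. Nothing below depends on it.

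**Inputs from the document.** 60 children, 20 per condition, both word types at every test, and a Poisson-type link.

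**Assumptions, not in the document.** Two-sided alpha 0.05; estimated child slopes with SD 1 for each word type; correlation r between a child's treated and control slopes of .3 to .7 (.3 to .5 in step 2); flat read as a non-significant control slope; slopes treated as approximately normal.

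**Step 1: chance of missing a real control drift.** For a true mean control slope of c SD, the one-sample t statistic has noncentrality c × √n. The chance of non-significance is the noncentral t probability between the critical values (±2.001 for n = 60, ±2.093 for n = 20).

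- n = 60, c = 0.2: noncentrality 1.549, missed in 66.8%.
- n = 60, c = 0.3: noncentrality 2.324, missed in 37.2%.
- n = 20, c = 0.2: noncentrality 0.894, missed in 86.4%; in all three conditions 0.864³ = 64.5%.
- n = 20, c = 0.3: noncentrality 1.342, missed in 75.3%; in all three conditions 0.753³ = 42.7%.

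**Step 2: two separate readings against one contrast, when the true slopes are equal.** Simulated t tests, 60 children, 40,000 trials per setting:

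| Common slope (SD) | r | Treated significant, control not | Direct contrast favours treated |
|---|---|---|---|
| 0.2 | .3 | 18% | 2.5% |
| 0.2 | .5 | 15% | 2.4% |
| 0.3 | .3 | 19% | 2.5% |
| 0.3 | .5 | 16% | 2.4% |
| 0.4 | .3 | 10% | 2.5% |
| 0.4 | .5 | 9% | 2.6% |

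A normal approximation gives 8% to 19% over the same settings. At a common slope of 0.5 SD it falls to 2% to 3%, because both slopes are then nearly always significant.

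**Step 3: what a direct contrast could detect.** With 80% power, the detectable difference is (1.960 + 0.842) × √(2(1 − r)/n).

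- All 60 children: 0.43, 0.36 and 0.28 SD at r = .3, .5 and .7.
- Within one condition of 20: 0.74, 0.63 and 0.49 SD.
- Difference of that contrast between two conditions of 20, multiplying the SE by a further √2: 1.05, 0.89 and 0.69 SD.

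The overall contrast is usable. The word type × time × condition contrasts are imprecise.

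**Step 4: scale.** Under a log link, control growth from 0.5 to 1 word and treated growth from 5 to 10 words both have slope log 2, although the gains are 0.5 and 5 words (illustrative counts). A word type × time test on the log scale could therefore show no difference where the gain in words differs tenfold.

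**The case against.** The strongest reply is that the research question is not threatened. Research Question 3.1 and its hypotheses compare low, medium and high testing. Children are randomised to those conditions, so maturation is balanced in expectation. This stands. A reader might infer that the condition comparison is confounded by maturation; the documents do not support that.

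A reader might also infer that the plan would declare controls flat whenever p exceeds 0.05. It states no such rule. It gives an expectation, and the word relatively may mean relative to treated words. The percentages therefore illustrate one plausible reading and are not the plan's operating characteristics. The drifts are in assumed SD units, and if control counts sit near zero a drift of 0.2 SD could be a small fraction of a word.

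It is also too strong to say that a general effect of testing would go unseen. A similar approach for control words implies a model that includes condition, and the text refers to trajectories in all three conditions. Such an effect during treatment would show there in part. What is missing is a formal comparison with treated words.

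After treatment, the hypothesised direction is decline, so upward maturation would work against that finding and could not create it. A reader might infer that maturation is more likely after treatment than during it. The document gives no treatment duration to compare with the 12 weeks.

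Finally, separate modelling is the natural reading of a similar approach, but it is not stated outright.

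**Conclusion.** The point holds as a worthwhile, inexpensive improvement to a secondary inference. The plan draws a treatment-versus-maturation conclusion that no planned contrast tests, although the data for one are collected at all 11 tests. The randomised low/mid/high slope contrast is valid as it stands and should remain primary.

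On the assumed reading of flat, drifts of 0.2 to 0.3 SD would pass unnoticed in about 67% to 37% of trials with 60 children. Equal slopes of 0.2 to 0.4 SD would produce the misleading pattern in about 9% to 19%, against about 2.5% for a direct contrast. These sizes depend on the assumed alpha, drift, correlation and normal slopes. The absence of a contrast, of a criterion for flat and of a post-treatment control-word growth model does not.

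**What to change.** For definition and naming, in the treatment phase and the post-treatment phase, fit treated and control words in one model. Include word type (treated/control), time, condition and their interactions, with child-level effects allowed to correlate across word types.

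- Base the treatment-versus-maturation statement on the treated-minus-control difference in change. Report it with a confidence interval, overall and by condition.
- State the scale in advance, for example model-based words gained, because equal slopes under a log link can hide very different gains.
- Present the word type × time × condition contrasts as supportive, given the limited precision with 20 children per condition.
- Keep the treated-word condition contrasts primary.
- If flatness is kept as a criterion, set a numeric bound for it before the data are analysed.

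The cost is programming and more covariance parameters, which may be hard to estimate if control counts are near zero. No additional testing or children are needed.

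### RQ3.3 chooses each early cut-off only to minimise false positives and judges it on the same 60 children, so specificity and LR+ look perfect at every test point and early benchmarks may be insensitive

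*Combined protocol and SAP*

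**What the plan says.** The combined protocol and SAP, Statistical models, Research Question 3.3, sets out four steps, separately for treatment and post-treatment and for definition and naming.

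1. Each child is labelled a success or not (learner, rememberer) at the last point in the series, using the accuracy range of the control words.
2. An appropriate cut-off is chosen at each earlier point. Because false positives are judged more costly than false negatives, "we will select cutoffs that minimize false positives". The cost judgement is referred to a progress report that is not among the documents.
3. Sensitivity, specificity, both likelihood ratios and both predictive values are calculated at each point.
4. "We will then determine the earliest point when we can accurately predict treatment and post-treatment outcomes".

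The Sampling Plan describes one sample: "Sixty kindergarten children with DLD will participate", "yielding 20 children per treatment condition". On existing data it says "N/A -- Not using existing data". The sample size rationale adds: "There is no specific power analysis for research question 3.3".

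The documents give no minimum sensitivity, maximum false-positive rate, cost ratio, tie-break or threshold for calling a prediction accurate. They mention no hold-out sample, cross-validation or bootstrap.

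**The concern.** A false positive here is a child predicted to succeed who does not. Raising the cut-off can only remove false positives, so a rule that counts nothing else always favours a higher cut-off and never penalises missed learners. Judging that cut-off on the children who determined it then fixes several of the accuracy measures in advance.

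RQ3.3 is meant to deliver benchmarks and the earliest point of accurate prediction, and the Hypotheses section expects accuracy to rise at each point. A measure that is perfect at reading 1 cannot show that rise. The benchmarks would also carry a false-positive rate of zero that new children will not reproduce. The RQ3.1 comparison of testing conditions is not affected.

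**Working it through.** The plan gives no figure for RQ3.3 to reproduce, so the check follows the rule through.

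**Inputs from the plan.** There are 60 children. Scores are counts out of 30, since "definition and naming data will be collected for 30 treated words and 30 control words". The early points are readings 1 to 5, and the immediate, 4-week and 8-week tests, each for two measures: (5 + 3) × 2 = 16 cut-offs.

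**Assumptions, because the plan is silent.** The correlation r between early and final score is .6 to .9, with .95 as an extension. The share of learners is 1/3, 1/2 or 2/3. Early and final scores are bivariate normal, with the early score rounded to 0–30 (mean 10, SD 6).

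**Step 1: what the rule selects.** Predict success if the score exceeds c. The number of false positives never increases with c. It is zero for every c at or above the highest non-learner score, so the rule has no unique solution. The most favourable choice is the lowest such c, which is the score of one child.

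**Step 2: apparent accuracy.** With zero false positives among m non-learners:
- specificity = m/m = 1.00;
- LR+ = sensitivity/(1 − specificity) = sensitivity/0, infinite if any child is predicted to succeed;
- PPV = TP/(TP + 0) = 1.00 under the same condition, and undefined if nobody is predicted to succeed.

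This holds at every test point. Only sensitivity, NPV and LR− (= 1 − sensitivity) can vary.

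**Step 3: false positives in new children.** For a continuous score, a new non-learner exceeds the highest of m non-learners with probability 1/(m + 1). For m = 40, 30 and 20 this is 1/41 = 2.4%, 1/31 = 3.2% and 1/21 = 4.8%. Rounding to whole words lowers it somewhat.

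**Step 4: simulation of the lowest zero-false-positive cut-off.** Cells show mean sensitivity / mean false-positive rate in new children.

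| r | 1/3 learners | 1/2 learners | 2/3 learners |
|---|---|---|---|
| .6 | .15 / 2.0% | .18 / 2.7% | .25 / 4.1% |
| .75 | .25 / 2.0% | .30 / 2.7% | .39 / 4.1% |
| .9 | .47 / 1.8% | .54 / 2.4% | .63 / 3.7% |
| .95 | .62 / 1.6% | .68 / 2.3% | .76 / 3.4% |

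At r = .75 with half learners, the 5th to 95th percentile range of sensitivity is .06 to .57. That spread reflects dependence on one child.

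**Step 5: true PPV and LR+ at r = .6 with half learners.** LR+ = .18/.027 = 6.7. PPV = .18/(.18 + .027) = .87. The apparent values are infinity and 1.00.

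**Step 6: does resampling remove the optimism?** In leave-one-child-out validation, only omitting the top non-learner lowers the cut-off enough to produce a false positive (barring ties). The validated rate is therefore 1/m. With m = 30 that is 3.3%, close to the expected 3.2%.

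**Step 7: a constrained rule, for illustration.** Taking the lowest cut-off with an apparent false-positive rate of at most 10%, mean sensitivity is about .40 to .78 over r = .6 to .9. The apparent false-positive rate is about 6 to 7.5%, and the rate in new children about 9 to 10%. Validation is therefore still needed under a better rule.

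**The case against.** The strongest reply is that the false-positive sentence should not be read alone. The plan asks for an appropriate cut-off, and it justifies the rule by relative cost, which implies that false negatives also count. It reports sensitivity at every point. A reader might infer that the plan commits to predicting that no child succeeds. The documents do not support that: such a cut-off would show a sensitivity of zero and is unlikely to be adopted.

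A reader might also infer that the test points cannot be ordered at all. That too goes too far, because sensitivity, NPV and LR− still separate early from late points, as the table shows. Nor is low sensitivity certain. Adjacent late points may correlate at .9 or more, where sensitivity is about .5 to .8.

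The understatement of the false-positive rate is modest on average. An exact 95% upper limit as high as 31% can be quoted for 0 of 10 non-learners. That is fewer non-learners than the 20 to 40 examined here, and the limit presupposes a cut-off fixed in advance.

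Finally, the progress report may contain the missing trade-off, and a looser rule would work against the investigators' stated preference.

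These points limit the size of the concern but do not remove it. If judgement of what is appropriate supplies the missing constraint, the cut-off is chosen after the data are seen. If the progress report supplies it, it belongs in the plan. Neither addresses the lack of validation, which is inferred from silence, but firmly: one sample is described and no existing data are used.

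**Conclusion.** The concern holds in this form. The written rule has no counterbalancing criterion in these documents, and its accuracy is judged on the children used to set it. Followed as written, even at its most lenient, it fixes apparent specificity at 1.00 at every point. It also makes LR+ infinite and PPV 1.00 wherever any child is predicted to succeed. This biases the result and goes beyond missing detail.

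Early benchmarks may be insensitive (about .15 to .63 under the stated assumptions, higher above r = .9). The false-positive rate in new children averages about 2 to 4%. The larger distortion is in PPV and LR+: about .87 and 7 at r = .6 with half learners. The correlations, the learner share and the score distribution are assumptions. The logic of steps 1 and 2 depends on none of them.

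The plan should be changed for RQ3.3, at a priority below anything that affects RQ3.1.

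**What to change.** 1. Replace the cut-off rule with: at each test point, choose the cut-off with the highest sensitivity among those whose false-positive rate does not exceed a maximum that the investigators fix in advance from their own cost judgement. Specificity of at least .90 is only an example; the documents give no basis for a particular value. If the progress report already contains the trade-off, copy it into the plan.
2. Fix now the sensitivity needed to call a point accurate.
3. Estimate sensitivity, specificity, likelihood ratios and predictive values by leave-one-child-out or bootstrap validation, repeating the cut-off selection in each resample. Report intervals.
4. Base the earliest accurate point on the validated values.

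The cost is a change of wording and a short resampling program, with no change to design or data collection. Reported accuracy will be slightly less favourable. If the maximum is above zero, more false positives are accepted: about 9 to 10% in new children at an apparent limit of 10%, against about 2 to 4% under the zero-false-positive rule. The investigators should weigh that against the gain in sensitivity.
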